8.2 Randomization

This is an open-label, non-randomized study.

9.0 Study Endpoints

9.1 Primary Endpoints

Phase 1b

- Characterization of DLTs
- MTD or RP2D dose of onvansertib in combination with either low-dose cytarabine or decitabine
- Characterization of AEs by incidence and severity (graded by NCI-CTCAE version 4.03)

Phase 2

- Safety And Tolerability
 - Characterization of AEs by type, incidence, severity (graded by NCI-CTCAE version 4.03), seriousness, and relationship to treatment
 - Effects on vital signs and laboratory parameters

- Frequency of dose interruptions, dose reductions, and treatment discontinuation
- Frequency of lab abnormalities
- Medical history
- Changes from baseline in ECGs, physical examinations, weight, and ECOG performance, echocardiograph (ECHO)/ multigated acquisition scan (MUGA)
- Efficacy
 - Rate of complete response (CR + CRi) in Phase 2, defined as a morphologic leukemia-free state (MLF; see below) plus:

For CR:

- Subject is independent of transfusions
- Absolute neutrophil count (ANC) of $>1000/\text{mm}^3$
- Number of platelets of $\geq 100,000/\text{mm}^3$

For complete response with incomplete blood count recovery (CRi):

- Meets all criteria for CR except for neutropenia ($\text{ANC} < 1000/\text{mm}^3$) or thrombocytopenia ($< 100,000/\text{mm}^3$) but must include transfusion independence

9.2 Secondary Endpoints

Phase 1b

- Characterization of AEs by incidence and severity (graded by NCI-CTCAE version 4.03)
- Concentrations of onvansertib in plasma samples collected at prespecified time points before and after administration of onvansertib, including maximum plasma concentration (Cmax), trough plasma concentration (Ctrough), time to maximum plasma concentration (Tmax), area under the concentration-time curve from 0 to time of last quantifiable concentration (AUClast), and plasma terminal elimination half-life (T-HALF)

Phase 2

- Note that Phase 2 analysis will only include onvansertib in combination with decitabine
- Characterization of AEs by incidence and severity (graded by NCI-CTCAE version 4.03)
- Concentrations of onvansertib in plasma samples collected at prespecified time points before and after administration of onvansertib, including maximum plasma concentration (Cmax), trough plasma concentration (Ctrough), time to maximum plasma concentration (Tmax), area under the concentration-time curve from 0 to time of last quantifiable concentration (AUClast), and plasma terminal elimination half-life (T-HALF)
- Efficacy
 - Rate of MLF in Phase 2, defined as:
 - Bone marrow (BM) $< 5\%$ blasts in an aspirate with spicules (a BM biopsy should be performed if spicules are absent)
 - No blasts with Auer rods or persistence of extramedullary disease
 - Rate of partial response (PR) in Phase 2: All of the hematologic values for a CR but with a decrease of at least 50% in the percentage of blasts to 5% to 25% in the bone marrow aspirate and a normalization of blood counts as noted above
 - Duration of response (DOR) in Phase 2: Time from documentation of response until documentation of recurrence of or progression of disease
 - Event-free survival (EFS) in Phase 2: Time from enrollment until disease

- progression or death from any cause
- o Overall survival (OS) in Phase 2: Time from enrollment until death from any cause

9.3 Exploratory Endpoints

- Blood samples for PD and diagnostic biomarker evaluation
- Evaluation of the rate of complete response (CR + CRI), MLF state, PR, DOR, EFS and OS in all enrolled subjects (Phases 1b and 2)
- Note that PRA will not receive PD or biomarker data and will not provide this evaluation

10.0 Conventions and Derivations

10.1 Study Day

Study day is defined as:

(study date – Cycle 1/Day 1 date +1)

Cycle 1/Day 1 is the start date of study treatment. Study days before the first administration of study treatment will be calculated as date of assessment minus date of first administration of study treatment. Every effort will be made to avoid missing and/or incomplete dates. In case of missing and/or incomplete dates no study days will be calculated.

10.2 Baseline

The baseline value is defined as the last measurement prior to the first dose of study drug on Day 1 of Cycle 1 (the earliest of onvansertib, plus low-dose cytarabine or decitabine). If assessment time is missing and there is no way to determine if the assessment occurred pre-dose, Cycle 1/Day 1 assessments will be considered for baseline, including for assessments occurring on Cycle 1/Day 1.

10.3 Change from Baseline

Change from baseline is defined as:

(value at post-baseline visit – value at baseline)

In summary tabulations over time, unscheduled post-baseline values will be excluded.

10.4 Past and Current Medical History

Past medical histories are those with a stop date prior to the first administration of study treatment.

Current medical histories are those which started prior to enrollment in the study but which are ongoing at the start date on or after the first administration of study treatment.

10.5 Prior and Concomitant Medications

Concomitant medications are all medications (or treatments) other than study drugs that are taken or received by the subject at any time during the study starting at the time that the first dose of study drug was administered through the end of study treatment. Use of all concomitant medications, including any change in therapy, will be recorded, categorized and summarized according to WHO Drug Global B3 SEP2017. Prior medications are medications that end prior to a subject's first dose of study drug. Prior and concomitant medications are medications that begin prior to a subject's first dose of study drug. Refer to [Section 10.11.1](#) for rules of imputing partial/missing concomitant medications start and stop dates.

10.6 Derivation of Efficacy Variables

The primary efficacy measure is leukemia response in Phase 2, which is evaluated at the timepoints indicated in the schedule of events in the clinical protocol (tables 9-1, 9-2, and 9-3) and is based on BM aspirate results and peripheral blood examinations. Response criteria will be based on the International Working Group for AML ([Cheson et. al. 2003](#)). Baseline efficacy assessments are required to be completed within 14 days of enrollment.

10.6.1 Rate of Complete Response

The primary efficacy variable is the rate of complete response (CR + CRI), where complete response is defined as follows:

CR

subject has MLF, plus:

- subject is independent of transfusions
- has an absolute neutrophil count (ANC) $>1000/\text{mm}^3$, and
- platelets $\geq 100,000/\text{mm}^3$

or

CRI

- subject meets all criteria for CR except for either neutropenia (ANC $<1000/\text{mm}^3$) or thrombocytopenia (platelets $<100,000/\text{mm}^3$) but also must include transfusion independence

CR or CRI are indicated on the Bone Marrow Aspirate Response CRFs as an Investigator Response of "Morphologic complete remission (CR)" or "Morphologic complete remission with incomplete blood count recovery (CRI)", respectively. The rate of complete response is defined as the proportion of subjects where best overall response (BOR) is CR or CRI at the 14 to 21 days post-treatment assessment.

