10.6.2 Rate of Achievement of a Morphologic Leukemia-Free State

Achievement of MLF is indicated by a 'Y' response to the "Morphologic leukemia-free state present?" field of the Bone Marrow Aspirate Response CRFs. The rate of achievement of MLF is defined as the proportion of subjects with MLF indicated at the 14 to 21 days post-treatment assessment.

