10.6.3 Rate of Partial Response

A Partial Response (PR) is indicated on the Bone Marrow Aspirate Response CRFs as an Investigator Response of "Partial response (PR)". The rate of partial response is defined as the proportion of subjects with a response of PR at the 14 to 21 days post-treatment assessment.

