10.6.4 Best Overall (Leukemic) Response

The Best Overall (Leukemic) Response (BOR) for each subject is defined as the best response per Investigator assessment among all responses recorded after start of treatment through to disease progression or end of treatment, whichever comes first, with a decreasing response ranking of CR, CRI, MLF state, PR, stable disease, then Treatment Failure. Stable disease and treatment failure are indicated as Investigator Responses on the Bone Marrow Aspirate Response CRFs.

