10.6.5 Duration of Response

The Duration of Response (DOR) is defined as the time in months from documentation of response until documentation of recurrence of or progression of disease, i.e.:

(date of documentation of recurrence or progression of disease – date of first observation of CR, CRi, MLF state, or PR + 1)/30.4375

Disease progression is captured on the Discontinuation CRF as a Reason for Discontinuation of “Progressive Disease” along with the Date of Discontinuation (progression of disease).

Recurrent disease is captured on the Discontinuation CRF as an Reason for Discontinuation of “Recurrent Disease” along with the Date of Discontinuation (progression of disease).

The DOR will only be calculated for the subgroup of subjects achieving CR, CRi, MLF state, or PR at the 14 to 21 days post-treatment assessment. Event times will be censored either on the date of the last evaluable assessment documenting response and recurrence-free or progression-free at the time of analysis or on date of death.

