13.5.1 Leukemic Response

The primary efficacy variable is leukemia response in Phase 2 subjects as evaluated by the Investigator at the end of each induction cycle, as indicated by the Investigator, and at the end of -study visit based on BM aspirate and peripheral blood examination results.

Responders are subjects with a CR or CRi accompanied by MLF state. Subjects without efficacy evaluable assessments will be considered non-responders in the ITT analysis population.

The count and proportion of Phase 2 subjects achieving CR, CRi, MLF state, PR, Stable Disease, or Treatment Failure as the best overall leukemic response will be summarized based on the ITT analysis set using counts and percentages.

Rate of complete response (CR+CRi) will be summarized for the ITT analysis set and exact 95% binomial confidence intervals generated.

The count of subjects with MLF state and PR will be summarized based on counts and percentages for the ITT analysis set. All efficacy tables will also be presented for the PP analysis set. Ninety-Five% exact CIs will be presented for the percentages. Similar summaries will be generated based on extramedullary disease.

BOR data will be provided in a listing.

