13.5.2 Duration of Response

DOR will be summarized using Kaplan-Meier (KM; [Kaplan and Meier 1958](#)) estimates for the ITT and PP analysis set in Phase 2 subjects who have had a response (CR, CRi, MLF state, or PR). The min, max, 25%, 50%, and 75% quartiles will be calculated and corresponding 95% CIs for the quartiles by the KM method. A KM plot for DOR will be presented. The count and percentage of responding subjects who have an event or are censored will be summarized.

DOR data will be provided in a listing.

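### The SAP gives conflicting rules for the primary CR + CRi rate: a single 14–21 day assessment, or every response recorded on treatment

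*SAP*

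**What the plan says.** Four derivations in the SAP carry a 14–21 day window:

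- Complete response (10.6.1): the "proportion of subjects where best overall response (BOR) is CR or CRI at the 14 to 21 days post-treatment assessment".
- Morphologic leukemia-free state, MLF (10.6.2): the "proportion of subjects with MLF indicated at the 14 to 21 days post-treatment assessment".
- Partial response, PR (10.6.3): the "proportion of subjects with a response of PR at the 14 to 21 days post-treatment assessment".
- Duration of response, DOR (10.6.5): calculated only for the "subgroup of subjects achieving CR, CRi, MLF state, or PR at the 14 to 21 days post-treatment assessment".

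Other SAP sections describe the same endpoints differently:

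- Section 10.6: response is "evaluated at the timepoints indicated in the schedule of events in the clinical protocol (tables 9-1, 9-2, and 9-3".
- Section 10.6.4: best overall response (BOR) is the "best response per Investigator assessment among all responses recorded after start of treatment through to disease progression or end of treatment", whichever comes first.
- Section 13.5.1: leukemia response is taken "as evaluated by the Investigator at the end of each induction cycle, as indicated by the Investigator, and at the end of -study visit".
- Section 13.5.2: DOR is summarized "in Phase 2 subjects who have had a response (CR, CRi, MLF state, or PR", with no limit on when the response occurred.

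The protocol (Sections 8.1.3 and 9.3.1) defines CR, CRi, MLF, PR and DOR without a time limit. In Protocol Table 9-3 (footnote f) and Section 9.2.2.2, a marrow 14 to 21 days after therapy starts is one of several assessments. It is done only where clinically appropriate, and its purpose is to document disease status. If the marrow is hypoplastic, remission is documented by a repeat marrow once blood counts recover. Further marrows follow before Cycle 3 and at alternate cycles after that. SAP Section 6.1, which lists departures from the protocol, does not mention a 14–21 day restriction.

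**The concern.** The SAP does not give one rule for its primary endpoint. The sentence in 10.6.1 contradicts its own term: BOR, as 10.6.4 defines it, looks across the whole treatment period and cannot also be confined to one early assessment. For MLF and PR there is no such tension, because the window is the entire rule.

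Two programmers could each follow this SAP and report different primary rates. Under the literal reading, a subject whose remission is first documented at count recovery or before Cycle 3 is a non-responder in the primary rate. In the BOR table that 13.5.1 places in the same report, that subject is a CR or CRi. A subject who never had the conditional early marrow could not be a responder at all, yet would stay in the ITT denominator. For DOR, later responders are excluded by 10.6.5 and included by 13.5.2.

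The trial is open-label with a single Phase 2 arm, so the choice between the rules must not be left until responses are known.

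**Working it through.** **1. The plan's own figures.** Protocol Section 12.3 assumes a CR + CRi rate p = 0.20 with n = 32. The standard error is √(0.20 × 0.80 / 32) = 0.0707.

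- 90% CI: half-width 1.645 × 0.0707 = 0.116; width 0.233; relative precision 0.116 / 0.20 = 58%. The plan states 0.23 and 58%.
- 95% CI: half-width 1.960 × 0.0707 = 0.139; width 0.277; relative precision 69%. The plan states 0.28 and about 70%.

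Both reproduce. They do not depend on the response window, but they describe the primary result only if the rate being estimated is the one assumed to be 20%.

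**2. The rules side by side.**

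| Endpoint | Windowed rule | Competing rule |
|---|---|---|
| CR + CRi | 10.6.1: at the 14–21 day assessment | 10.6.4: BOR to progression or end of treatment; 13.5.1: cycle ends plus end-of-study visit; protocol: no limit |
| MLF | 10.6.2: at the 14–21 day assessment | Protocol 8.1.3: no limit |
| PR | 10.6.3: at the 14–21 day assessment | Protocol 8.1.3: no limit |
| DOR entry | 10.6.5: responders at the 14–21 day assessment | 13.5.2: anyone who has responded |

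There is a second, smaller mismatch: 10.6.4 stops at end of treatment, while 13.5.1 also counts the end-of-study visit.

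**3. Direction.** A CR or CRi at the early marrow, on treatment and before progression, is also a CR or CRi by BOR. The reverse is not true. The windowed numerator is therefore a subset of the BOR numerator over the same ITT denominator, and the windowed rate can only be equal or lower.

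**4. Size.** Let f be the share of subjects with a BOR of CR or CRi whose response is already documented in the window. The documents do not give f, so the values below are assumptions. Expected responders under the literal rule = 32 × 0.20 × f = 6.4f.

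| f | Expected responders | Rate | Responders missed |
|---|---|---|---|
| 100% | 6.4 | 20% | 0 |
| 75% | 4.8 | 15% | 1.6 |
| 50% | 3.2 | 10% | 3.2 |
| 25% | 1.6 | 5% | 4.8 |
| 10% | 0.64 | 2% | 5.76 |

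In whole subjects, with the exact (Clopper-Pearson) 95% interval, the type named in 13.5.1:

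- 6/32 by BOR: 18.8% (7.2% to 36.4%).
- 5 of those 6 in the window: 5/32 = 15.6% (5.3% to 32.8%).
- 3 of those 6 in the window: 3/32 = 9.4% (2.0% to 25.0%).

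**5. Is f below 100% plausible?** CR requires ANC above 1000/mm³ and platelets of at least 100,000/mm³. CRi waives only one of the two counts and still requires transfusion independence. Protocol Section 10.1.4 treats marrow aplasia as expected with AML therapy. Protocol Section 6.1.3 reports, for the earlier solid-tumor study, a median Cycle 1 nadir at 14.5 days for platelets and 15 days for neutrophils, with median recovery 7 and 6.5 days later. Adding these gives 14.5 + 7 = 21.5 and 15 + 6.5 = 21.5 days, about the end of the window. This is indicative only: sums of medians are not medians of sums, and the data are from onvansertib alone in solid tumors.

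**The case against.** The best counter-argument is that the primary endpoint is the least affected of the four. Section 10.6.1 works through BOR, BOR is a defined term, and 13.5.1 also summarizes BOR. A careful programmer might let the definition govern, and the primary rate would then be unaffected. That is a reasonable reading, but nothing in the SAP makes it the rule. It also does nothing for MLF, PR and DOR entry, whose restriction is explicit.

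Second, the meaning of the window is uncertain. The SAP speaks of post-treatment, while the protocol times its early marrow from the start of therapy. Counted from the Day 5 dose, the window would be Days 19 to 26, and the wording could simply be a form label. This stands. The link to the protocol's early marrow is an inference, and the CRF and table shells are not available to settle it. An undefined anchor is itself a reason to correct the text.

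Third, Section 10.6 is compatible with either reading, because the schedules it cites include the early marrow, and 13.5.1 states other timepoints rather than none. That is fair. The sharpest contradictions are with 10.6.4, 13.5.2 and the protocol endpoint. The fault is in making one conditional assessment the only qualifying one.

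Fourth, f is assumed, no hypothesis test depends on the rate, and the required listings keep later responses visible. All true. This limits what can be said about size, but it does not decide which rate is primary.

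**Conclusion.** The conflict is real, and nothing in either document resolves it. As written, the SAP supports two different primary CR + CRi rates and two different DOR populations, and it applies an undeclared window to MLF and PR. Followed literally, the primary rate is biased downward relative to the protocol endpoint whenever any remission is first documented after the window.

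The direction is certain under that reading; the size is not known. Under the planning assumptions it runs from no effect (f = 100%) to half the planned rate (10% rather than 20% at f = 50%), and lower still if f is smaller. The estimate rests on the assumed 20% rate, 32 ITT subjects, and the inference that the window refers to the protocol's early marrow. Because the primary endpoint is involved, this should be corrected before database lock.

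**What to change.** Before database lock:

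1. Delete the 14–21 day wording from SAP Sections 10.6.1, 10.6.2, 10.6.3 and 10.6.5.
2. Define the CR + CRi rate as the proportion of Phase 2 ITT subjects whose BOR under 10.6.4 is CR or CRi.
3. Over the same assessment period, define MLF as a positive entry in the CRF field at any assessment, PR as a BOR of PR, and DOR entry as a BOR of CR, CRi, MLF or PR. State openly that a PR which later becomes a CR then counts only as a CR.
4. Use one end to the assessment period in both 10.6.4 and 13.5.1, and say whether a marrow at the end-of-study visit counts.
5. If early response is of interest, keep it as a separate descriptive row.

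If the window is in fact intended, list it in Section 6.1 as a change from the protocol, state what it is counted from, give the reason, and bring 10.6.4, 13.5.1 and 13.5.2 into line.

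The cost is wording in about six SAP sections. The later marrows are already in the protocol schedule, so no new data are needed. Any edits to the table shells or the CRF cannot be sized, because neither was available.

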10.6.2 Rate of Achievement of a Morphologic Leukemia-Free State

Achievement of MLF is indicated by a 'Y' response to the "Morphologic leukemia-free state present?" field of the Bone Marrow Aspirate Response CRFs. The rate of achievement of MLF is defined as the proportion of subjects with MLF indicated at the 14 to 21 days post-treatment assessment.

10.6.3 Rate of Partial Response

A Partial Response (PR) is indicated on the Bone Marrow Aspirate Response CRFs as an Investigator Response of "Partial response (PR)". The rate of partial response is defined as the proportion of subjects with a response of PR at the 14 to 21 days post-treatment assessment.

10.6.4 Best Overall (Leukemic) Response

The Best Overall (Leukemic) Response (BOR) for each subject is defined as the best response per Investigator assessment among all responses recorded after start of treatment through to disease progression or end of treatment, whichever comes first, with a decreasing response ranking of CR, CRI, MLF state, PR, stable disease, then Treatment Failure. Stable disease and treatment failure are indicated as Investigator Responses on the Bone Marrow Aspirate Response CRFs.

10.6.5 Duration of Response

The Duration of Response (DOR) is defined as the time in months from documentation of response until documentation of recurrence of or progression of disease, i.e.:

(date of documentation of recurrence or progression of disease – date of first observation of CR, CRi, MLF state, or PR + 1)/30.4375

Disease progression is captured on the Discontinuation CRF as a Reason for Discontinuation of “Progressive Disease” along with the Date of Discontinuation (progression of disease).

Recurrent disease is captured on the Discontinuation CRF as an Reason for Discontinuation of “Recurrent Disease” along with the Date of Discontinuation (progression of disease).

The DOR will only be calculated for the subgroup of subjects achieving CR, CRi, MLF state, or PR at the 14 to 21 days post-treatment assessment. Event times will be censored either on the date of the last evaluable assessment documenting response and recurrence-free or progression-free at the time of analysis or on date of death.

10.6.6 Event-free Survival

Event-free Survival (EFS) is defined as the time in months from enrollment until disease progression or death from any cause, i.e.:

(earlier of date of documentation of progression of disease or death – date of enrollment + 1)/30.4375

Disease progression is captured on the Discontinuation CRF as a Reason for Discontinuation of “Progressive Disease” along with the Date of Discontinuation (progression of disease). Deaths are captured on the Adverse Events or Survival Status CRFs. Event times will be censored on the date of the last evaluable assessment documenting response and progression-free at the time of analysis.

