8.2 Study Duration

The screening period will be up to 28 days prior to enrollment. Onvansertib administration in both phases can continue for as long as the subject has documented hematopoietic recovery and for as long as the Investigator considers that the subject is receiving clinical benefit without safety or tolerability issues. In addition, subjects may be escalated or de-escalated to doses or schedules that are considered safe and well tolerated, and in the best interest of the subject. Subjects will be followed for survival for up to 1 year after enrollment.

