9.3.1.5 Duration of Response

- Time from documentation of response until documentation of recurrence of or progression of disease.

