9.3.1.6 Event-free Survival

- Time from enrollment until disease progression or death from any cause

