13.5.3 Event-Free Survival

EFS will be summarized using KM estimates for the ITT and PP analysis set in Phase 2 subjects. The min, max, 25%, 50%, and 75% quartiles will be calculated and corresponding 95% CIs for the quartiles by the KM method. A KM plot of EFS will be presented. The count and percentage of those who have an event or are censored will be summarized. The EFS rate at 12 months and corresponding 95% CIs by the KM method will be presented.

EFS data will be provided in a listing.

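### The EFS derivation in SAP 10.6.6 omits the discontinuation reason 'Recurrent Disease', so a documented relapse need not count as an EFS event.

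*SAP*

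**What the plan says.** **EFS.** Protocol 9.3.1.6 defines it as "Time from enrollment until disease progression or death from any cause". SAP 10.6.6 keeps that definition and computes the time to the "earlier of date of documentation of progression of disease or death". For the data source it says "Disease progression is captured on the Discontinuation CRF as a Reason for Discontinuation of" 'Progressive Disease', and it takes deaths from the Adverse Events or Survival Status forms. The censoring rule is: "Event times will be censored on the date of the last evaluable assessment documenting response and progression-free at the time of analysis". SAP 13.5.3 plans Kaplan-Meier quartiles and a plot, and adds that "The EFS rate at 12 months and corresponding 95% CIs by the KM method will be presented".

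**DOR.** Protocol 9.3.1.5 defines it as "Time from documentation of response until documentation of recurrence of or progression of disease". SAP 10.6.5 gives the same source for progression and then adds: "Recurrent disease is captured on the Discontinuation CRF as an Reason for Discontinuation of" 'Recurrent Disease'. Either reason ends DOR.

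**Follow-up.** Protocol 8.2 says "Subjects will be followed for survival for up to 1 year after enrollment". Protocol 9.2.2.3 instead has survival contacts every 2 months for 1 year after treatment is completed.

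**The concern.** The form distinguishes progression from recurrence, and the DOR derivation uses both. The EFS derivation uses only the first. A programmer who follows 10.6.6 literally would select 'Progressive Disease' and death and nothing else.

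A responder whose leukemia returns and who leaves treatment as 'Recurrent Disease' would then be handled in one of two ways:

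- If a death is recorded later, the EFS event falls on the death date instead of the relapse date.
- If no death is recorded, the subject is censored at the last assessment showing response without progression. That date lies just before the relapse, so the censoring is informative.

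Both routes make EFS look longer than it was. They also leave two tables in one report that disagree on whether the same relapse is an event.

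**Working it through.** **1. The two derivations side by side**

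| Element | DOR (SAP 10.6.5) | EFS (SAP 10.6.6) |
|---|---|---|
| Definition and formula | recurrence or progression | progression or death |
| Discontinuation reasons used | 'Progressive Disease' and 'Recurrent Disease' | 'Progressive Disease' only |
| Censoring status | free of recurrence or progression | progression-free |

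Recurrence is absent from every element of the EFS column. SAP 13.5.3 adds no rule that brings it back.

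**2. Direction**

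Moving an event from relapse to a later death can only raise the Kaplan-Meier curve between the two dates. Censoring just before relapse removes a downward step; the small loss from the risk set between the last assessment and the relapse does not offset this on average. The direction therefore does not depend on the rates.

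**3. Size (illustration)**

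The plan states no EFS figure to reproduce. Inputs from the documents are N=32 in Phase 2 and a 20% CR+CRi rate (Protocol 12.3). Everything else is assumed:

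- response rate r = 20%, 30% or 40%;
- relapse possible from month 2, with median m = 4, 6 or 9 months after that;
- progression in non-responders, median 3 months;
- death after failure, median 5 months; death without failure, median 24 months;
- exponential times, with an assessment every 2 months.

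With relapse counted as an event, the 12-month rate has a closed form:

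S(12) = 2^(−12/24) × [ r × 2^(−(12−2)/m) + (1−r) × 2^(−12/3) ]

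- r = 0.20, m = 6: 0.7071 × [0.20 × 0.3150 + 0.80 × 0.0625] = 0.7071 × 0.1130 = 0.080
- r = 0.30, m = 6: 0.7071 × [0.30 × 0.3150 + 0.70 × 0.0625] = 0.7071 × 0.1383 = 0.098

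The rule as written was simulated with 400,000 subjects per scenario. A relapse coded 'Recurrent Disease' becomes an event at death if death falls within follow-up; otherwise it is censored at the last 2-monthly assessment before relapse. Follow-up to 12 months from enrollment, all relapses coded 'Recurrent Disease':

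| r | m (months) | 12-month EFS, relapse counted | As written | Median EFS (months) |
|---|---|---|---|---|
| 20% | 6 | 8.0% | 9.9% | 3.3 → 3.5 |
| 30% | 6 | 9.8% | 12.8% | 3.6 → about 4.0 |

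Over all nine combinations of r and m, the 12-month rate rises as follows:

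| Follow-up | All relapses coded 'Recurrent Disease' | Half coded so |
|---|---|---|
| 12 months from enrollment | 1.6 to 4.3 points | 0.8 to 2.1 points |
| 1 year after treatment stops (taken as failure) | 3.3 to 8.6 points | 1.6 to 4.1 points |

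Under the first follow-up rule with all relapses so coded, the all-subject median rises by 0.2 to 1.0 months.

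**4. Subjects involved**

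With λ = ln2/m and μ = ln2/24, the expected number of relapses within 12 months among 32 subjects is 32 × r × e^(−2μ) × λ/(λ+μ) × (1 − e^(−10(λ+μ))).

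- r = 0.20, m = 9: 6.4 × 0.944 × 0.727 × 0.653 = 2.9
- r = 0.40, m = 4: 12.8 × 0.944 × 0.857 × 0.868 = 9.0

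So about 3 to 9 of 32 subjects would have a relapse that does not count when it happens.

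**5. Dependence on assumptions**

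A cruder calculation gives a wider range. It uses relapse medians of 6 to 10 months, median death after relapse of 4 to 8 months, and no death without failure. It treats every relapse either as censored when it occurs or as ignored until death. The 12-month rate is then about 0.11 to 0.22 with relapse counted, and the literal rule adds roughly 0.04 to 0.18.

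**6. Against sampling error**

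At a 12-month rate near 10%, the 95% half-width is 1.96 × √(0.10 × 0.90 / 32) = 0.104, about ±10 points.

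**The case against.** The best counter-argument is that the documents use progression as an umbrella term that includes relapse. In 10.6.5 the date attached to 'Recurrent Disease' carries the parenthetical label 'progression of disease'. The protocol's removal and discontinuation lists (8.3.3 and 11.1) name progression and have no separate relapse criterion. Protocol 9.2.1.1 writes recurrence and progression as a single item. On that reading, 10.6.6 already covers relapse. How sites choose between the two reasons is also unknown: the form and table shells are separate documents, and the share of relapses coded 'Recurrent Disease' could be zero.

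This establishes ambiguity, not intent. Both DOR definitions treat recurrence and progression as two things, and no passage says that recurrence is progression for EFS. If inclusion was intended, 10.6.6 does not carry it out; if exclusion was intended, the plan should say so.

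Several limits do stand:

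- SAP 10.6.6 follows the protocol's EFS wording, so the gap is shared by both documents and is not an SAP departure.
- Relapses coded 'Progressive Disease' already count.
- The rates are assumed, and so is the 2-monthly assessment. The scheduled marrow before Cycle 3 and every other cycle thereafter implies 42 to 56 days with 21- to 28-day cycles and no delays.
- EFS is descriptive, and the subject listings would let a reader see the relapses.
- Adding the second reason would still not capture a relapse in a subject who stops for another reason, such as toxicity.

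**Conclusion.** The concern holds. As written, 10.6.6 does not make a relapse coded 'Recurrent Disease' an EFS event, although 10.6.5 makes it a DOR event. The resulting bias is upward. Its size depends on relapse and death rates that the documents do not give, on the share of relapses coded this way, and on which follow-up rule applies. Under the main assumptions the shift is systematic but smaller than the sampling error with 32 subjects. The CR+CRi analysis, OS and the sample size are untouched. This should be fixed, but it does not threaten the trial's main conclusion.

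**What to change.** In SAP 10.6.6:

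- Define the EFS event as the earliest of discontinuation for 'Progressive Disease', discontinuation for 'Recurrent Disease', or death from any cause.
- Date the first two by the Date of Discontinuation, as 10.6.5 does.
- Add recurrence to the date formula.
- Require subjects to be both recurrence-free and progression-free at the censoring date.

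In SAP 6.1, record that recurrence counts as progression for EFS, because the protocol definition does not say so.

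The cost is a few words in 10.6.6, one line in 6.1 and one extra condition in the EFS program. No new data are needed. The downside is a slightly less favourable EFS estimate. Making the change before database lock, when the SAP is due to be final, avoids choosing the event definition after results are known.
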